7.4. Pharmacodynamic Analyses

PD endpoints will be summarized by treatment arm at the primary analysis using the PD analysis set and at the final analysis by treatment sequence using All Cemdisiran Treated Analysis Set. Analyses of PD endpoints are summarized in Table 4 below.

Endpoint	Statistical Method	Notes
Change from baseline in C5 level over the course of the study	Absolute change and percentage change from baseline in C5 will be summarized descriptively and plotted over time by treatment arm or treatment sequence.	
Change from baseline in complement activity (Complement Alternative Pathway [CAP] and Complement Classical Pathway [CCP]) over the course of the study	The levels of CAP and CCP and the changes and percentage changes from baseline will be summarized descriptively and plotted over time by treatment arm or treatment sequence.	The biomarkers of complement activation include but not limited to C5a, sC5b9 in plasma, and sC5b9 in urine.

Table 4	Summary of Analyses	for Pharmacodynamic	Variables
---------	---------------------	---------------------	-----------

7.5. Pharmacokinetic Analyses

Pharmacokinetic analyses will be performed for cemdisiran and active metabolite, AS(N-2)3'-ALN-CC5 and AS(N-3)3'-ALN-CC5 cemdisiran, using noncompartmental methods. PK analyses will be performed at the final analysis based on the Pharmacokinetic Analysis Set. Summaries will be provided for each scheduled time point. PK data will be included in bypatient data listings. The following PK parameters will be estimated for each subject, as appropriate and if data permits: area under the concentration-time curve (AUC), maximum plasma concentration (C_{max}), time to maximum plasma concentration (T_{max}), terminal elimination half-life ($t^{1/2}\beta$), apparent clearance (CL/F), apparent volume of distribution (V/F), cumulative amount excreted unchanged in urine (Ae), and percent of dose excreted (fe). Additional PK parameters may be calculated, if deemed necessary. The PK parameters will be summarized using descriptive statistics.

Pharmacokinetic analyses will be conducted using noncompartmental methods. PK parameters will be calculated using a validated version of Phoenix® WinNonlin.

7.6. Safety Analyses

Primary safety analyses will compare cemdisiran versus placebo during the DB period using the Safety Analysis Set. Long-term safety analyses of cemdisiran will be summarized by treatment sequence (cemdisiran/cemdisiran, placebo/cemdisiran, all cemdisiran treated arm) using the all Cemdisiran Treated Analysis set.

The primary safety parameter is the frequency of treatment emergent adverse events (TEAEs). A TEAE is defined as an AE that occurred or worsened on or after the first dose of study drug through 28 days after the last dose of study drug. In addition, an AE that occurs after the 28 days from the last dose but is considered to be related to study drug, is considered to be a TEAE. Other safety parameters include vital signs, ECGs, clinical laboratory assessments, and physical exams. Adverse events that are non-treatment emergent (e.g., during safety follow up period) will be summarized and listed separately.

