5.2. General Methods

Categorical variables will be summarized by frequency and percentage in each category. Continuous variables will be summarized by the number of patients, mean, median, standard deviation (SD), interquartile range (Q1, Q3), minimum, maximum and geometric mean (GM) when appropriate. For log-transformed data, coefficient of variation (CV) and geometric mean (GM) will also be presented. CV is calculated as

 $\sqrt{\exp(\text{variance of log transformed data)} - 1 \times 100\%}$.

For the summary statistics of all numerical variables unless otherwise specified, minimum and maximum will be displayed to the same level of precision as reported. Median, mean, standard deviation and standard error will be presented to the level of precision collected in database plus one additional decimal.

Day 1 will be defined as the day of the first dose of study drug (cemdisiran or placebo). Study Day is relative to first dosing date of study drug for all patients.

• If the assessment date is after the date of first study drug dose, then the study day will be calculated as:

Study Day = Date of assessment - date of first dose of study drug + 1

• If assessment date is before the date of the first dose of study drug, then study day will be calculated as:

Study Day = Date of assessment – date of first dose of study drug

For patients who were randomized to placebo and switched to cemdisiran in OLE period, an additional study day will be defined which reflects the study days relative to the first dose of cemdisiran.

For laboratory parameters, any assessments recorded as lower than the lower limit of quantification (LLOQ) will be replaced by the respective LLOQ value. Any assessment recorded as greater than the upper limit of quantification (ULOQ) will be replaced by the respective ULOQ value. For assessments with repeated collections at a given study visit (e.g. ECG parameters) the mean will be used as the value at the visit for all parameters.

For all analysis sets except for the All Cemdisiran Treated Set, summaries will be presented by treatment arm (cemdisiran and placebo). For the All Cemdisiran Treated Set, summaries will be presented by the following treatment sequence groups:

- Cemdisiran / Cemdisiran: all patients who received cemdisiran during the DB period, including patients who continued to receive cemdisiran during the OLE period and patients who discontinued treatment during the DB period

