5.3. Baseline Definitions

Baseline value for 24-hour UP, UPCR, and UACR will be calculated as the average of two valid (as per section 6.4.1.1 of the protocol) collections at week -2 visit (i.e., the last measurement prior to the first dose of study drug). Baseline values for vital signs will be defined as the assessments at week -2 visit because of the required vaccination when applicable. The baseline value for an ECG variable (heart rate, PR interval, QRS interval, QT interval or QT_c interval) will be the average of last triple assessments prior to the first dose of study drug (Day 1). For other parameters, baseline is defined as the last non-missing value prior to the first dose date/time of the study drug, unless otherwise specified.

For the All Cemdisiran Treated Set, baseline for patients randomized to cemdisiran in DB period is as defined above. For patients who switched from placebo in the DB period and received at least one dose of cemdisiran in the OLE period, baseline for all parameters will be redefined as the last non-missing assessments prior to the first dose of cemdisiran, except for assessments based on 24-hour urine collections where the average of the two valid collections at week 32 visit will be the baseline value and for ECG variables where the average of the last triplet assessments prior to the first dose of study drug in OLE period will be the baseline.

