5.10. Primary and Final Analyses

The study includes a 36-week DB period, a 156-week OLE period, and a 52-week safety follow up period. The primary analysis is to evaluate the efficacy and safety of cemdisiran compared to placebo during the DB period.

For the primary analysis, tables and figures will be presented by treatment arm (cemdisiran, placebo). Selected outputs will also be summarized by treatment sequence (cemdisiran/cemdisiran, placebo/cemdisiran and all cemdisiran treated). When assessments or AE onset dates are exactly the first dose date in the OLE period with time missing, the records will be included in the OLE period. Per-patient listings will include all data collected during the entire study. The listings will be sorted by randomized arm. Within patient, there will be a variable to indicate the period of the data collection.

Final analysis evaluating the long-term efficacy and safety of cemdisiran will be described for the All Cemdisiran Treated Set. Summary tables and figures will be presented by treatment sequence (cemdisiran/cemdisiran, placebo/cemdisiran and all cemdisiran treated).

For patients who received placebo in the DB period and switched to cemdisiran in the OLE period, the intra-patient comparison of the two treatment periods will be conducted for 24-hour UP, 24-hour UPCR, spot UPCR and eGFR in the final analysis. The time period during which patients receiving cemdisiran (i.e. on or after the first date/time of cemdisiran) is referred as "during cemdisiran treatment".

The detailed definitions for different study periods are as the following:

• DB Period

It is defined as the time between the first dose of study drug and Week 36/end of study (EOS) visit. For patients who do not have the Week 36/EOS visit, it is the time between the first dose of study drug and the targeted Week 36/EOS visit (Day 252).

• OLE Period

The start date of the OLE period is defined as the first dose of cemdisiran of the OLE period (i.e., week 36 visit) and ends at week 188/EOS visit.

• Safety Follow-up Period

The 52-week safety follow-up period starts at week 36/EOS visit (for patients not continuing into the OLE) or week 188/EOS visit.

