6.3. Medical History, Prior and Concomitant Medications

Medical history, prior and concomitant medications will be summarized for the Safety Analysis Set.

The medical history data will be coded with the Medical Dictionary for Regulatory Activities (MedDRA version 21.1 or higher). The number and percent of subjects by System Organ Class (SOC), high level term (HLT) and Preferred Term (PT) will be summarized by treatment group and overall. Prior and concomitant medications will be coded with the World Health Organization (WHO) Drug Dictionary (September 2018 or later).

Prior medications are defined as medications that were taken prior to the first dose of study drug (cemdisiran or placebo). Concomitant medications are defined as medications which were taken prior to and were ongoing while on study drug or medication(s) taken on or after the first dose date of the study drug.

Tabular summary of the number and percentage of subjects taking concomitant medications will be summarized by anatomic therapeutic class (ATC) and preferred term. Listing will be provided for medical history, prior and concomitant medications.

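### Section 7.6 starts the TEAE window at the first dose of cemdisiran or placebo and sets no cemdisiran start for the All Cemdisiran Treated Set, so crossover patients' placebo-period events literally count in the long-term columns

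*SAP*

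**What the plan says.** Section 7.6 sets up two safety analyses: cemdisiran against placebo in the double-blind period, and a long-term part in which "Long-term safety analyses of cemdisiran will be summarized by treatment sequence" using the All Cemdisiran Treated Set. It then gives a single TEAE definition with no qualifier for period or analysis set: "an AE that occurred or worsened on or after the first dose of study drug through 28 days after the last dose" of study drug, plus later events considered related.

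Study drug is glossed twice as either treatment. Section 5.2 says "Day 1 will be defined as the day of the first dose of study drug (cemdisiran or placebo"), and Section 6.3 defines prior medications as "medications that were taken prior to the first dose of study drug (cemdisiran or placebo"). Section 5.6 judges missing or partial AE onset dates against the same first dose of study drug.

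Section 4.1 defines the All Cemdisiran Treated Set by patients, not by time at risk, and expressly includes those who took placebo first and then switched.

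For those patients the SAP does restart other clocks. Section 5.3 states that "baseline for all parameters will be redefined as the last non-missing assessments prior to the first dose of cemdisiran", with exceptions for 24-hour urine and ECG values. Section 5.2 adds a second study day counted from first cemdisiran, and Section 5.7 re-maps their open-label visits in the same way. Section 5.10 defines a period called *during cemdisiran treatment*, but Sections 7.6, 7.6.1 and 7.6.2 never use that term.

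**The concern.** For a crossover patient the first dose of study drug is a placebo dose. An event in the placebo period therefore meets the TEAE definition, and no sentence removes it from the long-term tables. The same holds for an event that began on placebo and continued unchanged.

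The All Cemdisiran Treated Set exists to describe the long-term safety of cemdisiran, and its adverse event tables would attribute placebo-period events to the drug. Because Section 7.6.1 renames TEAEs as AEs for the rest of the document, the same start date carries into the severity, relatedness, SAE and discontinuation tables and into the injection-site and hepatic summaries of Section 7.6.2. Site staff are blinded in the double-blind period (Section 2.3), so a placebo event could be judged drug-related and then appear as treatment-related in a cemdisiran column.

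At the least, two programmers working from this SAP could produce different long-term tables.

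**Working it through.** **Text check.** The SAP states no figure to reproduce. The question is which start date applies to a placebo/cemdisiran patient:

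| Item | Section | Start for crossover patients |
|---|---|---|
| Study day | 5.2 | Additional day from first cemdisiran |
| Baseline | 5.3 | Before first cemdisiran |
| Visits | 5.7 | Re-mapped to first cemdisiran |
| TEAE window | 7.6 | First study drug, i.e. placebo |
| Incomplete AE onset dates | 5.6 | First study drug, i.e. placebo |
| Exposure, All Cemdisiran Treated Set | 6.4 | Similar to the double-blind period; start not stated |

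The first three were restarted explicitly; the AE rules were not.

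**Size, as an illustration.** Inputs from the SAP:

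- Planned arms of 20 cemdisiran and 10 placebo (Section 2.1).
- Double-blind period of 36 weeks (Section 5.10).
- Open-label period from Week 36 to Week 188 (Section 5.10), so 188 − 36 = 152 weeks. The same section also calls it 156 weeks, so both are shown.

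Assumptions: every placebo patient crosses over, everyone has the same follow-up, and the event rate is constant.

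Let L be the open-label weeks. The ratio of events counted literally to events counted from first cemdisiran is:

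- placebo/cemdisiran: (36 + L) / L
- All Cemdisiran: 30(36 + L) / [20(36 + L) + 10L]

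| L (weeks) | Placebo/cemdisiran | All Cemdisiran |
|---|---|---|
| 152 | 188/152 = 1.24 | 5640/5280 = 1.07 |
| 156 | 192/156 = 1.23 | 5760/5400 = 1.07 |
| 52 (assumed) | 88/52 = 1.69 | 2640/2280 = 1.16 |
| 12 (assumed) | 48/12 = 4.0 | 1440/1080 = 1.33 |

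Placebo time is 10 × 36 = 360 patient-weeks. At L = 152 that is 36/188 = 19.1% of the placebo/cemdisiran window and 360/5640 = 6.4% of the pooled window.

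These are ratios of event counts. They do not carry over to the percentages of patients in the overview table. For those, a term seen in 3 of the 10 crossover patients on placebo, and in none of those three on cemdisiran, would add 3/30 = 10 percentage points to the pooled column.

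Cemdisiran/cemdisiran patients are unaffected, because their first study drug dose is their first cemdisiran dose.

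**The case against.** The best reply is that a TEAE flag and a table's period are separate steps. The double-blind table is limited to its own period although the TEAE window runs on into the extension, so the long-term tables may have an implied limit too. Section 7.6 calls them long-term safety analyses of cemdisiran. Section 5.10 assigns AEs dated exactly on the first open-label dose, with time missing, to the open-label period, which presupposes a split at that point. It also defines *during cemdisiran treatment*, and Section 5.7 uses a near-identical phrase to scope summaries.

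This stands as evidence of intent. It does not close the gap, because none of these texts restricts the adverse event tables by sequence. Nor do sequence columns imply cemdisiran time only: Section 7.6.4 plans selected liver tests by sequence across the double-blind and open-label periods together.

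Three stronger readings are tempting but unsupported:

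- **Off-drug follow-up enters the TEAE tables** because *during cemdisiran treatment* has no stated end. It does not: Section 7.6 ends the window 28 days after the last dose, apart from related events, and reports non-emergent events separately.
- **Exposure-adjusted rates mismatch numerator and denominator.** This is not established. Section 7.6.1 refers to exposure in the respective period, and if both parts include placebo time, the constant-rate assumption gives a rate ratio of 1.0.
- **A 4-fold inflation at the Week 36 lock.** That needs 12 open-label weeks per crossover patient, which the SAP does not state. It also needs AE tables among the outputs shown by sequence then; Section 5.10 says only "Selected outputs will also be summarized by treatment sequence (cemdisiran/cemdisiran, placebo/cemdisiran and all cemdisiran treated").

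**Conclusion.** The point holds as a defect in a stated rule. Section 7.6 uses one TEAE start for all safety analyses, and for crossover patients that start is a placebo dose. Taken literally, their placebo-period events enter the placebo/cemdisiran and All Cemdisiran columns, contrary to how the SAP treats study day, baseline and visits and to what Section 5.10 suggests was meant.

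The inflation in event counts is about 1.24-fold in placebo/cemdisiran and 1.07-fold pooled, given planned numbers, 152 open-label weeks for all and a constant rate. The pooled effect at full follow-up is modest and grows if open-label follow-up is shorter.

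The double-blind comparison is untouched, no AE rates are tested statistically, and the sequences also appear in separate columns. It should be corrected because it concerns the primary safety parameter in the set meant to describe long-term safety, and because the present text permits two different sets of tables.

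**What to change.** Add to Section 7.6: for the All Cemdisiran Treated Set, a TEAE is an AE with onset or worsening on or after the first dose of cemdisiran; the existing 28-day and related-event rules are unchanged.

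Then align three places for this set:

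- **Section 5.6:** judge missing or partial AE onset dates against the first dose of cemdisiran.
- **Section 6.4:** state that exposure starts at the first dose of cemdisiran.
- **Section 7.6.1:** state that exposure-adjusted rates use that exposure time.

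The cost is a sentence in Section 7.6, matching phrases in the other sections and one programming flag. No new data are needed and the double-blind outputs do not change.

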7.6.1. Adverse Events

All TEAEs hereafter will be referred to as AEs in this document. No statistical tests will be performed to compare AE rates between treatment groups. Adverse events will be coded using MedDRA version 21.1 or higher and displayed in tables using SOC and PT.

An overview table of AEs will be tabulated. The overview table will include the number and percentage of patients in following categories such as, but not limited to:

- At least 1 AE
- At least 1 study drug related AE
- At least 1 severe AE
- At least 1 study drug related severe AE
- At least 1 Serious Adverse Event (SAE)
- At least 1 study drug related SAE
- At least 1 AE leading to treatment discontinuation
- At least 1 study drug related AE leading to treatment discontinuation
- At least 1 AE leading to study withdrawal
- At least 1 study drug related AE leading to study withdrawal
- Death

Tabulations by SOC and PT displaying the number of patients (percentage) and total events will be produced for the following tables:

- All AEs
- Severe AEs
- AEs by Maximum Severity
- AE related to treatment
- AEs related to treatment by Maximum Severity
- All SAEs
- SAEs related to treatment
- AEs leading to treatment discontinuation
- AEs leading to treatment interruption
- AEs leading to study withdrawal

Tabulations by PT in decreasing order in frequency within the cemdisiran arm will be generated for the following tables:

- All AEs
- All SAEs

- AEs related to treatment
- SAEs related to treatment

In summaries by SOC and PT, AEs will be sorted alphabetically by SOC then by PT.

There will also be an overall AE table generated displaying rates of adverse events adjusted for exposure-time during the respective period. Patients who report multiple occurrences of the same AE (preferred term) will be classified according to the most severe occurrence or most related.

Separate listings will be provided for deaths, SAEs, and AEs leading to discontinuation of study drug, withdrawal of study drug, and/or dose interruption. By-subject AE listings will be provided.

7.6.2. Adverse Event of Clinical Interest (AECI)

Additional summaries of safety areas of interest based on Standardized MedDRA Queries (SMQs) and other groupings of AEs may be summarized such as, but not limited to the following:

• Injection Site Reactions [ISRs]: AEs mapping to the High-Level Term (HLT) = "Injection Site Reactions" using MedDRA dictionary will be included in the summary.

Frequency (percentages) of ISRs by HLT and PT will be generated. A separate listing will be generated to display all patients who reported ISRs. A table will also be generated to display the number of patients with at least 1 ISR, total number of doses (any dose split into multiple injections will be considered 1 dose in summary), total number of doses with ISRs, and the signs and symptoms reported due to ISRs. If there are multiple ISRs that occur in between two consecutive injections, then these events will be considered as 1 ISR and considered related to the earlier injection.

• Hepatic AEs, including AEs of LFT abnormalities: These AEs are mapped to the SMQ Drug-related hepatic disorders - comprehensive search (includes all narrow and broad terms).

Frequency (percentages) of drug-related hepatic disorders will be summarized by SOC, HLT and PT. A separate listing will be generated of all patients reporting these events.

7.6.3. Laboratory Data

Clinical laboratory parameters will be expressed in Standard International (SI) units. Summaries will only include data from central laboratory. For any local collections of LFTs, these will be included in a separate data listing. Key laboratory parameters will be graded according to NCI CTCAE v5.0.

Summaries for each lab parameter (hematology, chemistry, liver function tests, coagulation and urinalysis), which are continuous variables, will have a tabular summary of descriptive statistics

at each scheduled visit. Descriptive statistics include actual value, change from baseline and percent change from baseline at each scheduled visit.

Shift tables will be generated to summarize shifts from baseline categories to the worst postbaseline categories with directionality specified for any labs which could be reported in either direction (e.g. above the upper limit of normal [ULN] or below ULN).

Clinical laboratory tests with normal ranges will be classified as Low, Normal, and High. For these tests, abnormal values will be flagged in the listings with H when the value is higher than the upper limit of the reference ranges and with L when the value is lower than the lower limit of the reference ranges.

For hematology and chemistry labs, summary tables of potentially clinically significant abnormalities will also be provided.

All laboratory data will be presented in data listings. Separate listings will be included for those laboratory data collected from local labs such as LFTs. Out of range laboratory results will be identified in listings.

7.6.4. Liver Function Analysis

A listing will be generated for all patients with abnormal liver function tests as defined by ALT>3xULN, AST>3xULN and total bilirubin >2x ULN at any visit.

A tabular summary for LFTs will be generated to summarize the number and associated percentage of patient in each of the categories at any post-baseline visit:

- ALT>1 & ≤3, ALT>3 & ≤5, ALT>5 & ≤10, ALT>10 & ≤20, ALT>20xULN
- AST>1 & ≤3, AST>3&≤5, AST>5& ≤10, AST>10 & ≤20, AST>20xULN
- ALT or AST>1 & ≤3, ALT or AST>3 & ≤5, ALT or AST>5 & ≤10, ALT or AST>10 & ≤20, AST or ALT>20xULN
- WNL, ALP>1.5xULN
- Total Bilirubin>1.5& ≤2, Total Bilirubin>2&≤3, Total Bilirubin>3& ≤5 and Total Bilirubin>5

eDISH plots of peak total bilirubin at any time versus peak ALT or AST at any time will also be presented. For selected labs (e.g. ALT/ULN and AST/ULN), a table and figure of the values across the entire study (DB+OLE) will be generated by treatment sequence arms.

